13.3.3.2 Analysis of Secondary Efficacy Variables

ACR50-CRP, ACR70-CRP response at Week 12

The response rate of the ACR50-CRP is defined as the subjects achieving an ACR50-CRP response divided by the total number of subjects included in the FAS, with a similar

definition for the ACR70-CRP. Non-responder imputation will be applied. The response rate at Week 12 will be summarized by the randomized treatment group and the 95% CI of the response rate difference for each treatment group compared to placebo will be calculated using the M&N method, a score-based interval.⁵³

Remission based on DAS28-4(CRP) at Week 12

Remission as defined by DAS score is DAS28-4(CRP) score lower than 2.6. The DAS remission rate will be assessed at Week 12. Non-responder imputation will be applied. The response rate at Week 12 will be summarized by the randomized treatment group and the 95% CI of the response rate difference for each treatment group compared to placebo will be calculated using the M&N method. 53

ACR Hybrid Scores at Week 12

The ACR hybrid score is designed to combine the ACR20, ACR50, and ACR70 response score with the mean % improvement in all of the 7 individual ACR components, and is a more sensitive measure of change. The % improvement or worsening in each component is limited to 100%. If the mean % improvement is ≥20% in a subject who did not meet ACR20 criteria, the ACR hybrid score is limited to 19.99; similarly for ACR50 and ACR70. Conversely, if the mean % improvement is <20% in a subject who met ACR20 criteria, the ACR hybrid score is 20.00; similarly for ACR50 and ACR70.

For the change from baseline of ACR hybrid score, the linear mixed effect model for repeated measures will be applied. It includes treatment dose group and visit as fixed effects, subject as random effect, with adjustment of baseline ACR hybrid score and prior anti-TNF use as covariates. The difference of ACR hybrid score for each treatment group comparing to placebo at Week 12 will be estimated. The corresponding 95% CIs of the differences from placebo will be provided.

Change from Baseline in Physical Function at Week 12

Physical Function is assessed using the HAQ-DI and the Physical Function subscale of the SF-36. The following analyses apply to both. The linear mixed effect model for repeated measures will be applied. It includes treatment dose group and visit as fixed effects, subject as random effect, with adjustment of baseline scores and prior anti-TNF use as covariates. The difference of scores for each treatment group comparing to placebo at Week 12 will be estimated. The corresponding 95% CIs of the differences from placebo will be provided.

Change from Baseline in Physical Component Summary (PCS) score and Mental Component Summary (MCS) score from the SF-36, at Week 12

For the change from baseline for PCS score and MCS score at Week 12, the linear mixed effect model for repeated measures will be applied. It includes treatment dose group (placebo, 100 mg, 200 mg, 300 mg VX-509) as main effect, with adjustment of baseline scores and prior ant-TNF use as covariates. The difference of scores for each treatment group comparing to placebo at Week 12 will be estimated. The corresponding 95% CIs of the differences from placebo will be provided.

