SF Cell count/differential sample	X		X				
SF VX-509 PK sample	X		X				
Frozen SF sample	X		X				
Synovial Tissue (ST) samples	(Synovial	Biopsy Sub	set only; allo	cated in des	scending or	der of priority):	
ST Immunohistochemistry/ histopathology sample	X		X				
ST RNA sample	X		X				
ST Protein extraction sample	X		X				
Pharmacogenomic Assessmen	nts	•	•	•			
DNA Sample A (optional)	X						
DNA Sample B (optional)	X						
RNA Sample (optional)	X	X	X	X		X	X
Efficacy Assessments				1			
MRI on designated hand				X		X ^b	
Tender/swollen joint counts	X	X		X	X	X	X
Physician Global Assessment of Disease Activity	X	X		X	X	X	X
Subject Global Assessment of Disease Activity	X	X		X	X	X	X
Subject assessment of pain (VAS)	X	X		X	X	X	X
Subject assessment of general health (VAS)	X	X		X	X	X	X
Subject assessment of disability (Health Assessment Questionnaire – Disability Index [HAQ-DI])	X	X		X	X	X	X
Subject assessment of health- related quality of life (Short Form Health Survey [SF-36])	X			X		X	X

anti-CCP: anti-cyclic citrullinated peptide; BMI: body mass index; CRP: C-reactive protein;

ECG: electrocardiogram; IVRS/IWRS: Interactive Voice Response System/Interactive Web Response System;

JAK: Janus kinase; MRI: magnetic resonance imaging; PK: pharmacokinetic; RA: rheumatoid arthritis;

SF: synovial fluid; ST: synovial tissue; WESR: Westergren erythrocyte sedimentation rate.

Baseline is the most recent evaluation before the first dose of study drug on Day 1.

- Subjects who discontinue treatment early will be asked to return to the clinical research unit to complete the procedures specified for Week 12/Early Treatment Termination. If the subject discontinues before completing 3 weeks of treatment, the MRI will not be repeated.
- Subjects will receive their respective oral dose of VX-509 or placebo for 12 weeks. VX-509 should be administered at approximately the same time every day, throughout the study.
- A complete physical examination will be performed at the time points indicated. For all other scheduled visits, a symptom-directed physical examination assessment may be performed if indicated.
- ^e Subjects must abstain from all food and drink (except water) at least 8 hours before blood draws for the fasting lipid profile.
- Leptin and lipoprotein (a) will be assessed as part of the fasting lipid testing at this visit.

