8.2 Secondary Endpoints

- Proportion of subjects who achieve ACR50-CRP and ACR70-CRP responses at Week 12.
- Proportion of subjects with DAS28-4(CRP) <2.6, and those who achieve a remission, moderate response or good response according to the European League Against Rheumatism (EULAR) response criteria at Week 12.
- ACR hybrid scores at Week 12.

- Change from baseline in Health Assessment Questionnaire –Disability Index (HAQ-DI) at Week 12.
- Change from baseline in the Physical Function subscale of the 36-item Short Form (SF-36) at Week 12
- Change from baseline in the Physical Component and Mental Health Components of the SF-36 at Week 12
- Change from baseline in OMERACT RAMRIS synovitis, bone marrow edema (osteitis), erosion scores at Week 6.
- PK parameters of VX-509 and its metabolite in plasma (maximum observed concentration $[C_{max}]$ and area under the concentration versus time curve [AUC]).
- Safety and tolerability as indicated by adverse events, laboratory tests, electrocardiograms (ECGs) and vital signs.

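### The ACR hybrid score model adjusts for a baseline hybrid score that, by the protocol's own definition, is undefined or 0 for every subject

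*Protocol*

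**What the plan says.** Protocol Section 13.3.3.2 defines the ACR hybrid score as ACR20/50/70 status combined "with the mean % improvement in all of the 7 individual ACR components, and is a more sensitive measure of change". It bounds the inputs ("The % improvement or worsening in each component is limited to 100" percent) and ties the score to responder status: when the mean improvement reaches 20% "in a subject who did not meet ACR20 criteria, the ACR hybrid score is limited to 19.99", with matching rules at the other thresholds.

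The analysis paragraph that follows states: "For the change from baseline of ACR hybrid score, the linear mixed effect model for repeated measures will be applied". Dose group and visit are fixed effects, with "subject as random effect, with adjustment of baseline ACR hybrid score and prior anti-TNF use as covariates".

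The endpoint lists in Sections 2 and 8.2 give only "ACR hybrid scores at Week 12". Nearby items in those lists (HAQ-DI, SF-36, RAMRIS) are worded as changes from baseline; this one is not. The footnotes to Table 3-2 say that "Baseline is the most recent evaluation before the first dose of study drug on Day 1". The protocol does not define a baseline hybrid score anywhere.

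**The concern.** Every input to the hybrid score is already relative to baseline. The model sentence treats the score as if it were a level, like DAS28-4(CRP) or HAQ-DI, with its own pre-dose value to subtract and adjust for. It follows the same pattern as the models for those measures in Sections 13.3.3.1.2 and 13.3.3.2, where the pattern is correct, so this looks like template carry-over.

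Three things are at stake:
- The analyst must decide how to code a quantity that does not exist, and one of the two codings empties the model.
- Under the other coding, the stated baseline adjustment disappears without anyone having chosen to drop it.
- A replacement covariate chosen later, possibly with data in view, can move the estimates when there are about 10 subjects per arm.

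**Working it through.** The protocol gives no power, sample size or precision figure for this endpoint, so there is none to reproduce. The check is structural.

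**1. The score at baseline.** For component j with baseline B_j and current value X_j, percent improvement is 100 × (B_j − X_j) / B_j, limited to ±100 (Section 13.3.3.2). At baseline X_j = B_j, so each of the 7 components gives 100 × 0 / B_j = 0 and the mean is 0. ACR20 requires at least 20% improvement (Section 16.10), so it is not met. The cap of 19.99 does not bind, because 0 < 19.99. The baseline score is 0 for every subject, with variance 0. The alternative is to regard it as undefined, since no earlier reference value is specified.

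**2. Reading A: undefined, coded as missing.** The covariate is missing for all subjects, and so is the outcome, because a change needs a baseline. No record can enter the model.

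**3. Reading B: coded as 0.**
- Outcome: score − 0 = score, so the change is the score itself.
- Week 12 design matrix: intercept (1) + dose contrasts (3) + prior anti-TNF use (1) + baseline hybrid (1) = 6 columns. The last column is all zeros, so the rank is 5 and its coefficient cannot be estimated.
- Dose contrasts: unaffected. In a simulated dataset of 40 subjects (10 per arm, score coded from Sections 13.3.3.2 and 16.10), the three contrasts with placebo were 4.79, 7.39 and 18.46 both with and without the covariate. These values only illustrate the point and predict nothing about the trial.

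**4. What a real baseline covariate could add.** The documents give no correlation between any baseline measure and the hybrid score, so r is an assumption, taken over 0.2 to 0.4. Residual variance is multiplied by (1 − r²). Estimating one more coefficient inflates it by about 1 + 1/(residual df − 1). In a Week 12 approximation, residual df = 40 − 6 = 34, so the factor is 1 + 1/33 = 1.03.

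| Assumed r | 1 − r² | × 1.03 | Net reduction in variance |
|---|---|---|---|
| 0.2 | 0.96 | 0.99 | about 1% |
| 0.4 | 0.84 | 0.87 | about 13% |

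**5. Endpoint against model.** Sections 2 and 8.2 name the score at Week 12. In Section 13.3.3.2 the subheading and the contrast to be estimated also concern the score at Week 12. Only the model sentence and its covariate refer to a change from baseline and a baseline value.

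**The case against.** The best defence is that the slip is harmless. With the baseline score set to 0, standard software drops the empty column, the outcome is the score, and the estimated contrast is the one the endpoint list calls for. That stands: under this reading no treatment estimate changes. It also stands that each component is already scaled to the subject's own baseline, that prior anti-TNF use stays in the model, and that Section 13.1 says the study is not powered for comparisons with placebo.

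A reader might infer that the analysis cannot run at all. The documents do not support that; it follows only if the baseline score is coded as missing, and the protocol does not say how to code it. A reader might also take the variance figures above as the damage done by the error. They are not: they show what a different covariate might add under an assumed correlation.

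Two further defences are weaker. The first is that a hybrid score from screening to Day 1 could serve as the baseline, since the components are collected at screening (Table 3-1). No such score is defined, and the Table 3-2 footnote fixes baseline as the last pre-dose evaluation, which is the reference for change. The second is that the SAP will settle it. But the protocol does not leave a gap here; it fixes an outcome and a covariate that do not fit the score. A SAP that copies the sentence repeats the error, and one that corrects it departs from the protocol.

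**Conclusion.** The point holds as a specification error in one sentence. The baseline hybrid score carries no information under either reading, and calling the outcome a change from baseline conflicts with the endpoint in Sections 2 and 8.2. This follows from the protocol's own definition and needs no outside source.

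Its reach is limited to one secondary endpoint, and no stated sample size or power figure depends on it. Under the zero coding the dose contrasts stand, and what is lost is the baseline adjustment the protocol says it makes. Whether a real covariate would improve precision noticeably cannot be settled from the documents: the net 1% to 13% rests on an assumed r of 0.2 to 0.4 and on the single-visit approximation. The reason to correct it is that the model should be well defined, and its covariate named, before unblinding.

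**What to change.** Rewrite the model sentence in Section 13.3.3.2, and carry the same wording into the SAP:
- Take the hybrid score itself at each post-baseline visit as the outcome, matching Sections 2 and 8.2.
- Delete the baseline hybrid score as a covariate.
- Prespecify in its place a measure that exists at baseline. Baseline DAS28-4(CRP) is one candidate, already collected and already used in Section 13.3.3.1.2. Keep prior anti-TNF use.

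The minimum correction is the first two items; the third restores the baseline adjustment that the protocol evidently meant to make. The cost is one sentence and one degree of freedom relative to a model without the empty covariate, with no new data.

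Whether the models should include a treatment-by-visit term, and whether they should adjust for the randomisation stratum rather than prior anti-TNF use, are questions for all the mixed models in Sections 13.3.3.1.2, 13.3.3.1.3 and 13.3.3.2. They should be raised separately.

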9 STUDY DESIGN

9.1 Overview of Study Design

This is a Phase 2, randomized, placebo-controlled, double-blind, dose-ranging, multicenter study of VX-509 in subjects with moderate to severe RA who are seropositive or have demonstrated erosive disease, and an inadequate response to a DMARD.

Subjects who have been on a stable dose of DMARD (Section 10.3) must have a swollen joint count of ≥ 6 out of 66 assessed joints and a tender joint count of ≥ 8 out of 68 assessed joints, and a CRP level $\geq 1.2 \times$ the upper limit of normal (ULN) or Westergren erythrocyte sedimentation rate $\geq 1.2 \times$ ULN to qualify for the trial. MRI of the most swollen hand (2+ synovitis of wrist or ≥ 2 MCPs) at baseline will be performed before dosing and at Weeks 6 and 12. A subset of approximately 6 (no more than 10) subjects will undergo arthroscopic synovial biopsies before the first dose at baseline (Day 1) and at Week 4 (Synovial Biopsy Subset).

Subjects will be randomized with stratification based on prior use of biological response modifiers (including a tumor necrosis factor [TNF] inhibitor). VX-509 will be coadministered with DMARD for a planned duration of 12 weeks. Approximately 40 subjects will be randomized to 1 of 4 dosing regimens at a 1:1:1:1 ratio. VX-509-matched placebo tablets will be used to maintain the double-blind. As an exception, the subjects in the Synovial Biopsy Subset will only be randomized to the 200 mg qd dose of VX-509 (Arm C). Subjects in the Synovial biopsy Subset will know that they are not receiving placebo, but not the dose they are receiving.

Arm A. Placebo (N = 10)
Arm B. 100 mg VX-509 qd (N = 10)
Arm C. 200 mg VX-509 qd (N = 10)
Arm D. 300 mg VX-509 qd (N = 10)

The protocol has optional interim analyses (IA) for the purpose of selecting appropriate dose(s) for a subsequent pivotal trial (Section 13.3.4.7). No changes in study design or conduct will be made based on the results of an IA.

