13.3.3.1.2 Change from Baseline in DAS28-4(CRP)

For the change from baseline in DAS28-4(CRP) at Week 12, the linear mixed effect model for repeated measures will be applied. It includes treatment dose group (placebo, 100 mg, 200 mg, 300 mg VX-509) and visit as fixed effects, and subject as random effect, with adjustment of baseline DAS28-4(CRP) and prior anti-TNF use as covariates. The difference in DAS28-4(CRP) at Week 12 compared to placebo for each treatment group will be estimated. The corresponding 95% CI of the difference from placebo will be provided. A dose-response trend test will be performed at Week 12.

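### The PCS/MCS model in Section 13.3.3.2 is named a repeated-measures mixed model, but its listed terms omit visit and subject, so it does not define the Week 12 difference it promises

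*Protocol*

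**What the plan says.** Section 8.2 lists as a secondary endpoint: "Change from baseline in the Physical Component and Mental Health Components of the SF-36 at Week 12". Section 13.3.3.2 gives its analysis: "For the change from baseline for PCS score and MCS score at Week 12, the linear mixed effect model for repeated measures will be applied". The terms then listed are the four dose groups "as main effect, with adjustment of baseline scores and prior ant-TNF use as covariates". The target follows: "The difference of scores for each treatment group comparing to placebo at Week 12 will be estimated", with 95% CIs.

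The paragraph directly above covers HAQ-DI and the SF-36 Physical Function subscale under the same model name and gives a fuller list: "It includes treatment dose group and visit as fixed effects, subject as random effect, with adjustment of baseline scores and prior anti-TNF use as covariates". In Section 13.3.3.1.2 the DAS28-4(CRP) model likewise has dose group "and visit as fixed effects, and subject as random effect, with adjustment of baseline DAS28-4(CRP) and prior anti-TNF use as covariates". Both the RAMRIS model (Section 13.3.3.1.3) and the ACR hybrid model (Section 13.3.3.2) follow the same pattern.

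Table 3-2 schedules the SF-36 on Day 1, at Week 6, at Week 12 or early termination, and at the Safety Follow-up Visit. On numbers, Section 9.1 says: "Approximately 40 subjects will be randomized to 1 of 4 dosing regimens at a 1:1:1:1 ratio".

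**The concern.** A repeated-measures analysis needs something that links records from the same subject and something that separates one visit from another. The PCS/MCS term list has neither, while the adjacent paragraph for the same questionnaire has both. Someone programming from this text has to guess whether the shorter list is deliberate, and the guesses lead to different estimates and different intervals.

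PCS and MCS carry the secondary objective on physical and mental health-related quality of life (Section 7.2), and the planned result is the set of 95% CIs against placebo. With about 10 subjects per arm, both the target of the estimate and the width of the interval depend on how the gap is filled.

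**Working it through.** The protocol states no power, CI width or sample size for PCS or MCS, so there is no figure to reproduce. The check compares the term lists and then follows each reading through.

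**1. Term lists side by side**

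| Endpoint | Dose group | Visit | Subject | Baseline, prior anti-TNF use |
|---|---|---|---|---|
| DAS28-4(CRP) | yes | yes | random | yes |
| RAMRIS scores | yes | yes | random | yes |
| ACR hybrid | yes | yes | random | yes |
| HAQ-DI, SF-36 Physical Function | yes | yes | random | yes |
| SF-36 PCS, MCS | yes | not listed | not listed | yes |

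**2. Records per subject.** From Table 3-2, there are two post-baseline SF-36 scores at the treatment-period visits (Weeks 6 and 12) and a third at follow-up. The protocol does not say which of these enter the PCS/MCS model. The figures below use Weeks 6 and 12 only.

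**3. Reading A: a subject effect is inferred from the model's name.** The CI then allows for within-subject correlation. With no visit term there is one dose coefficient for all visits. With complete data and a random intercept it estimates (d6 + d12)/2, where d6 and d12 are the differences from placebo at Weeks 6 and 12. This equals d12 only if d6 = d12. Adding visit as a main effect moves the overall level at each visit but leaves one common dose difference, so it does not isolate Week 12 either.

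**4. Reading B: the listed terms are fitted literally to both records.** For m records per subject with variance σ² and common correlation ρ, the variance of a subject's mean is σ²(1 + (m − 1)ρ)/m. The pooled fit takes it as σ²/m. Hence

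- width ratio (reported to correct) = 1/√(1 + (m − 1)ρ)
- approximate coverage = 2Φ(1.96 × ratio) − 1

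The protocol gives no ρ. Taking 0.3 to 0.8 as an assumption, with m = 2:

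| ρ | Width ratio | Approximate coverage |
|---|---|---|
| 0.3 | 1/√1.3 = 0.88 | 91% |
| 0.5 | 1/√1.5 = 0.82 | 89% |
| 0.7 | 1/√1.7 = 0.77 | 87% |
| 0.8 | 1/√1.8 = 0.75 | 86% |

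A simulation agrees in direction and size (10 per arm, two visits, no dose effect, 400 trials per value of ρ; widths in SD units):

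| ρ | Pooled fit: width, coverage | With subject effect: width, coverage |
|---|---|---|
| 0.3 | 1.28, 0.91 | 1.50, 0.96 |
| 0.5 | 1.27, 0.87 | 1.61, 0.95 |
| 0.7 | 1.26, 0.83 | 1.71, 0.95 |

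The simulated width ratios (1.28/1.50 = 0.85, 1.27/1.61 = 0.79, 1.26/1.71 = 0.74) fall slightly below the formula. One reason is that the pooled fit also claims more residual degrees of freedom (80 − 6 = 74, against 40 − 6 = 34 at subject level). Adding visit to the model with a subject effect left widths (1.50, 1.61, 1.71) and coverage unchanged. The narrowing therefore comes from the missing subject effect alone. The missing visit structure affects what is estimated (reading A).

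**5. Reading C: Week 12 scores only.** With one record per subject, the listed terms are those of an ANCOVA. The difference is at Week 12 and the CI is valid, but nothing is repeated and the model's name is wrong.

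**The case against.** A reader might infer that the protocol treats a subject's repeated scores as independent and that the PCS and MCS intervals are therefore too narrow. The text does not support that. The same paragraph names a mixed model for repeated measures, and a model with no random effect and no within-subject covariance is not one. The list is introduced as what the model includes, which need not be exhaustive. Section 13.3 leaves methodological details to the SAP, which is not shown here and may settle the matter. The listed terms also fit a valid Week 12 ANCOVA. This argument stands, so the narrow interval is a conditional result.

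Two further inferences also go too far. One is to add the Safety Follow-up score as a third record, which would enlarge the distortion; nothing in the protocol puts that score into this model. The other is to speak of false-positive findings; for PCS and MCS the section specifies estimates and CIs, not a test.

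The objection does not remove the inconsistency. The protocol is not silent on this model: it states a term list that conflicts with the model's name, with its Week 12 target and with the paragraph above it. Reading the subject effect back in repairs the interval but still does not yield a Week 12 difference.

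**Conclusion.** The point holds as an internal inconsistency in the stated specification. With several records per subject, neither way of completing the PCS/MCS model gives a sound Week 12 comparison. An inferred subject effect gives a difference averaged over visits. A literal pooled fit of Weeks 6 and 12 gives a 95% CI about 0.88 to 0.75 of its correct width. That range rests on an assumed within-subject correlation of 0.3 to 0.8, equal for all subjects, with complete data. Only a Week 12-only fit is valid, and it contradicts the repeated-measures label.

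Severity is low to moderate. PCS and MCS are secondary endpoints, and Section 13.1 says the study is not powered to show significant changes against placebo.

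**What to change.** Replace the PCS/MCS term list in Section 13.3.3.2 with one of two complete specifications:

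- **Repeated measures:** dose group, visit and dose-by-visit as fixed effects; subject as random effect (or an unstructured within-subject covariance); adjustment for baseline score and prior anti-TNF use; difference from placebo and 95% CI taken at Week 12. State which visits enter.
- **Week 12 ANCOVA:** one record per subject, with dose group, baseline score and prior anti-TNF use, and the repeated-measures label dropped.

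Copying the HAQ-DI sentence unchanged is not enough, because visit as a main effect alone leaves a single dose difference across visits.

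The cost is one sentence in the protocol or SAP, with no new data or subjects. The CIs may be wider than under a literal pooled fit. With Weeks 6 and 12 the first option adds (4 − 1) × (2 − 1) = 3 interaction parameters to a model for about 40 subjects. The second makes no use of the Week 6 scores.
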